# 4.3.2 Long Term Treatment Phase (12 weeks or 52 Weeks)

Once completing the Screening/Observational Period, patients will return to the study site for the Baseline Visit. Patients who continue to meet all inclusion/exclusion criteria and have been compliant with the eDiary may enter the Long Term Treatment Phase. At the Baseline Visit, patients will be dispensed study medication and will be instructed they cannot take study medication until baseline laboratory results confirm study eligibility. After the investigator reviews the results of the baseline laboratory assessments and determines the patient's continued eligibility, the site staff will inform the patient whether or not they are eligible to start dosing in the Long Term Treatment phase. This contact with the patient must be documented in the patient's medical record.

There are two different dosing schedules in this study. If eligible, patients in the 2-8 moderate to severe migrains/month and 9-14 moderate to severe migraines month groups will be instructed that they can take study medication at the onset of a migraine (of mild to severe intensity). Patients will also be instructed that they can take a maximum of one tablet of

rimegepant per calendar day during the Long Term Treatment Phase at the onset of a migraine (mild, moderate or severe intensity).

Patients in the 4-14 moderate to severe migraines/month group will be instructed that they must take one tablet of study drug every other calendar day, regardless of whether they have a migraine on that day or not. If patients in this group have a migraine on a day that they are not scheduled to dose with rimegepant, they may take a rimegepant tablet to treat a migraine of mild, moderate or severe intensity. Therefore, patients can take a maximum of one tablet of rimegepant per calendar day for 12 weeks.

The electronic patient diary will be completed by patients to capture dosing of study medication and the frequency and severity of migraines during the Treatment Phase.

Patients will also use the eDiary to complete the Preference of Medication (PoM) and Satisfaction with Medication (SM) questionnaire. The Migraine-Specified Quality of Life questionnaire v 2.1 (MSQoL), The Sheehan Suicidality Tracking Scale (S-STS), Migraine Assessment Disability (MIDAS) and Clinical Global Impression (CGI-c) will be completed, or administered by the investigator, on paper at specified study visits (Table 1 and Table 2).

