2 STUDY DESIGN

2.1 Synopsis of Study Design

BHV3000-201 is a Phase IIb, multicenter, open-label study designed to assess the safety and tolerability of long-term use of rimegepant, taken up to one tablet per calendar day, in patients with migraine.

The Screening phase includes a Screening Visit and a 30-day Observation Period (OP). For subjects to be eligible for the study, they must have 2-14 migraine attacks of moderate to severe intensity per month in the 3 months prior to the Screening Visit. Patients enrolled in the every other day (EOD) dosing group must have had 4-14 migraine attacks of moderate to severe intensity per month within the 3 months prior to the Screening Visit. Enrollment into this study will initially be open to patients with 2-8 moderate to severe migraine attacks per month (primarily the patients from BHV3000-301 and BHV-3000-302) for approximately 3 months. After approximately 3 months, study enrollment will open for patients with a history of 9-14 migraine attacks of moderate to severe intensity per month within the 3 months prior to the Screening Visit. Lastly, study enrollment will open for subjects (including patients from BHV3000-303) in the EOD dosing group (4-14 moderate to severe migraines per month).

After providing informed consent, patients will first participate in the Screening phase to determine eligibility for the study. At the Screening Visit, patients will be given an electronic diary (eDiary) to document on each day of the OP if a migraine occurred, intensity, and if it was treated. They will also be given a paper diary to record the standard of care migraine treatment.

After completing the OP, patients will return to the clinic for their Baseline Visit, where enrollment into the Long-Term Treatment (LTT) phase will commence and eligibility for continued participation in the study will be determined before study medication is dispensed. After the investigator reviews the results of the baseline laboratory assessments and determines continued eligibility, the site staff will inform the patient whether or not they are eligible to start

dosing in the Long-Term Treatment (LTT) phase in the 2-8 or 9-14 moderate to severe migraines/month group followed for 52 weeks, or the 4-14 moderate to severe migraines/month group followed for 12 weeks.

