4.2.6 Subpopulations

The subgroups of interest for this study are the following:

- Intrinsic factors
 - Age: categorized as < 40, \geq 40, < 65, \geq 65
 - Sex: female, male
 - Sex and age: female < 40, female \geq 40, male < 40, male \geq 40
 - Race: white, black or African American, other including Asian, Asian
 - Ethnicity: Hispanic or Latino, not Hispanic or Latino
- Extrinsic disease-related factors
 - CV risk contraindicating triptans: yes, no (see Section 5.2.2)
 - Baseline body mass index (BMI; kg/m²): categorized as < 25, \geq 25 to < 30, \geq 30
 - Prophylactic migraine medication use on or after study drug start: yes, no (see Section 4.9)
- Extrinsic exposure factors
 - Time on rimegepant (weeks): categorized as quintiles for treated subjects (see Sections 4.8.1 and 5.2.3)

- Cumulative rimegepant exposure (tablets): categorized as quintiles for treated subjects (see Sections 4.8.1 and 5.2.3)
- Key factors
 - Average rimegepant exposure (tablets per 4 weeks): categorized as < 2, ≥ 2 to < 8, ≥ 8 to < 14, ≥ 14 for treated subjects (see Section 4.8.1)
 - Average rimegepant exposure (tablets per 4 weeks) for EOD+PRN treated subjects: categorized as < 14, ≥ 14 (see Section 4.8.1)
 - Treated subjects who took ≥ 14 tablets per 4 weeks for ≥ 12 weeks: categorized by enrollment group (see Section 4.8.1)
 - Treated subjects who took ≥ 20 tablets per 4 weeks for ≥ 4 weeks: categorized by enrollment group (see Section 4.8.1)
 - Treated subjects with near-daily dosing, defined as those in the (1) PRN dosing groups who took ≥ 14 tablets per 4 weeks for ≥ 12 weeks (see previous bullet), or (2) EOD+PRN dosing group: categorized by enrollment group.

Subgroup levels may be combined or redefined based on the availability of the data.

Subgroup tabulations will be by subgroup level and overall for treated subjects with non-missing subgroup level data. Refer to the BHV3000 Core SAP for rounding rules.

The triptan non-responder (yes, no) subgroup will be derived according to Section 5.2.1, included in the subgroup summary table (see Section 4.5), and excluded from subgroup tabulations by subgroup level and overall.

4.2.7 *Withdrawals, Dropout and Loss to Follow-Up*

Subjects who withdrew from the study were not replaced.

4.2.8 *Missing, Unused and Spurious Data*

Analyses will be based on observed data only.

4.3 *Planned Analyses*

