Drug accountability is provided by the site on the Drug Accountability CRF.

A by-subject listing will present eDiary exposure (i.e., number of tablets taken) and drug accountability for treated subjects.

Another by-subject listing will present eDiary exposure (i.e., total number of tablets taken) in 4-week intervals during the LTT for treated subjects. This will also display cumulative rimegepant exposure from both sources (i.e., eDiary and drug accountability), and flag subjects with ≥ 10 cumulative tablet difference between the 2 sources.

Another by-subject listing will present batch numbers for treated subjects.

eDiary Exposure

eDiary exposure will be summarized descriptively for treated subjects by enrollment group and overall, and will include the following parameters:

- Time in the OP (weeks), defined as (OP end date – OP start date + 1)/7
- Time from enrollment to last contact (weeks), defined as (last contact date – IWRS enrollment date + 1)/7
- Time in the LTT period (weeks), derived as (LT_T end date – LT_T start date + 1)/7
- Time on rimegepant (weeks), derived as (study drug end dose date – study drug first dose date + 1)/7.*
- Cumulative rimegepant exposure (tablets), derived by summing number of tablets across records with complete dates for subjects who reported taking study medication during the treatment epoch in the eDiary.*
- Average rimegepant exposure (tablets per 4 weeks), derived as 4*cumulative rimegepant exposure/time in the LTT period.*
- Number and percentage of subjects in the average rimegepant exposure (tablets per 4 weeks) categories defined in Section 4.2.6, and also in the following categories:
 - ≥ 12.6 ($\geq 90\%$ compliant with EOD dosing)
 - ≥ 11.2 ($\geq 80\%$ compliant with EOD dosing)
- Number and percentage of subjects who took more than 1 tablet per day on any day. This could be from the same bottle or different bottles due to an unscheduled visit.
- Exposure over time, as defined by the number and percentage of subjects who took
 - ≥ 8 tablets per 4 weeks for 4, 8, 12, 16, 20, ≥ 24 , ≥ 12 , and ≥ 4 weeks. These categories correspond respectively to 1, 2, 3, 4, 5, ≥ 6 , and ≥ 3 4-week intervals that are not necessarily consecutive (see below)
 - ≥ 12 tablets per 4 weeks for 4, 8, 12, 16, 20, ≥ 24 , ≥ 12 , and ≥ 4 weeks
 - ≥ 13 tablets per 4 weeks for 4, 8, 12, 16, 20, ≥ 24 , ≥ 12 , and ≥ 4 weeks

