 - ≥ 14 tablets per 4 weeks for 4, 8, 12, 16, 20, ≥ 24 , ≥ 12 , and ≥ 4 weeks (the “ ≥ 12 weeks” category will support the subgroup “treated subjects who took ≥ 14 tablets per 4 weeks for ≥ 12 weeks” specified in Section 4.2.6)
 - ≥ 20 tablets per 4 weeks for 4, 8, 12, 16, 20, ≥ 24 , ≥ 12 , and ≥ 4 weeks
 - ≥ 25 tablets per 4 weeks for 4, 8, 12, 16, 20, ≥ 24 , ≥ 12 , and ≥ 4 weeks
- Total rimegepant exposure (tablets) summed across all subjects, derived by summing cumulative exposure across all subjects
- Total rimegepant exposure (patient-years), derived by summing (study drug end dose date – study drug first dose date + 1)/365.25 across all subjects.

This summary will also display quintiles (e.g., P20, P40, P60, P80, where “PX” denotes Xth percentile) for asterisked (“*”) continuous parameters to support the derivation of rimegepant exposure subgroups (see below). See Section 5.3 for derived dates.

eDiary exposure over time will assess the number of 4-week (28-day) intervals in which a subject exceeded select tablet counts in the LTT analysis period (see Section 5.4), where the number of 4-week intervals are not necessarily consecutive. For example, suppose a subject takes 20 tablets through 4 weeks (interval 1; LTT study days 1 to 28), 10 tablets after 4 weeks to 8 weeks (interval 2; LTT study days 29 to 56), 25 tablets after 8 weeks to 12 weeks (interval 3; LTT study days 57 to 84), and 15 tablets after 12 weeks to 16 weeks (interval 4; LTT study days 85 to 112). Thus, this subject is considered to have taken ≥ 14 tablets per 4 weeks for 12 weeks (i.e., intervals 1, 3 and 4), ≥ 20 tablets per 4 weeks for 8 weeks (i.e., intervals 1 and 3), and ≥ 25 tablets per 4 weeks for 4 weeks (i.e., interval 3). See Section 5.5 for the definition of LTT study days.

eDiary exposure will also be summarized by subgroup level and overall for treated subjects for all subgroups of interest described in Section 4.2.6.

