5.3 Derived Dates

Derived dates for defining analysis periods are defined as follows:

- OP start date/time: Earliest complete date during the screening epoch in the eDiary.
- OP end date/time: Latest complete date during the screening epoch in the eDiary.
- LTT start date/time: Earliest complete date during the treatment epoch in the eDiary.
- LTT end date/time: Latest complete date during the treatment epoch in the eDiary.
- Study drug first dose date/time: Earliest complete date where subjects indicated that they took medication during the treatment epoch in the eDiary.
- Study drug end dose date/time: Latest complete date where subjects indicated that they took medication during the treatment epoch in the eDiary.
- Study drug last dose date/time: Study drug end dose date derived only for subjects who have non-missing completion status on the Study Exit Status CRF. Thus, in an interim analysis, all post-treatment data will be included for a subject who is still on study. At the last database lock, the last dose date will be equal to the end dose date for treated subjects.
- EOT visit date: Maximum of the following: (1) LTT end date/time; (2) latest complete visit date excluding folder name “follow-up safety visit” on the Visit Date CRF. This is derived only for subjects who have non-missing completion status on the Study Exit Status CRF.

- Last contact date: (1) Complete death date, if it exists; (2) otherwise, the maximum complete date of the following: AE start/stop; ECG; eDiary; enrollment; informed consent; laboratory collection; non-study medication start/stop; physical measurement; procedure; rating scale; questionnaire; screening; study completion/discontinuation; vital sign; visit.

No imputations are performed on these derived dates. Complete dates are those with valid, non-missing day, month, and year.

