5.5 Analysis Visit Windows

Refer to Protocol Section 4.3 for the schedule of assessments.

Study days are calculated from enrollment as follows:

- Measurement date – IWRS enrollment date + 1, if measurement date \geq IWRS enrollment date
- Measurement date – IWRS enrollment date, if measurement date $<$ IWRS enrollment date

Follow-up days are calculated from the EOT visit as follows:

- Measurement date – EOT visit date + 1, if measurement date \geq EOT visit date
- Measurement date – EOT visit date, if measurement date $<$ EOT visit date

Evaluation intervals are based on study days derived in the post-enrollment analysis and follow-up analysis periods (see Section 5.4). [Table 5](#) and [Table 6](#) have analysis visit windows for the PRN and EOD+PRN dosing groups, respectively.

Table 5: Analysis Visit Windows: 52-Week PRN (2-8) and (9-14) Dosing Groups

Visit	Analysis-Specified Interval for PoM, SM, MSQoL, MIDAS, and CGI-C	Analysis-Specified Interval for Other Endpoints	Target Day
Screening Period			
Screening	≤ -1	≤ -1	
Baseline	1	1	1
Post-Enrollment Period			
Week 2		2 to 21	14
Week 4		22 to 42	28
Week 8		43 to 70	56
Week 12	43 to 126	71 to 98	84
Week 16		99 to 126	112
Week 20		127 to 154	140
Week 24	127 to 210	155 to 182	168
Week 28		183 to 210	196
Week 32		211 to 238	224
Week 36	211 to 308	239 to 266	252
Week 40		267 to 294	280
Week 44		295 to 322	308
Week 48		323 to 350	336
Week 52	≥ 309	351 to 378	364
Week 56		≥ 379	392
Follow-up			
Follow-up Week 2		8 to 21	14
Follow-up Week 4		≥ 22	28

Study days are used for screening and post-enrollment; follow-up days are used for follow-up.

Table 6: Analysis Visit Windows: 12-Week EOD+PRN and PRN (2-8) Dosing Groups

Visit	Analysis-Specified Interval for PoM, SM, MSQoL, MIDAS, and CGI-C	Analysis-Specified Interval for Other Endpoints	Target Day
Screening Period			
Screening	≤ -1	≤ -1	
Baseline	1	1	1
Post-Enrollment Period			
Week 2		2 to 21	14
Week 4		22 to 42	28
Week 8		43 to 70	56
Week 12	≥ 43	71 to 98	84
Week 16		99 to 126	112
Follow-up			
Follow-up Week 2		8 to 21	14
Follow-up Week 4		≥ 22	28

Study days are used for screening and post-enrollment; follow-up days are used for follow-up.

LTT study days are used in analyses of migraine days and exposure, and are calculated from LTT start as follows:

- Measurement date – LTT start date + 1, if measurement date ≥ LTT start date
- Measurement date – LTT start date, if measurement date < LTT start date.

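### The EOD+PRN average-exposure cut of 14 tablets per 4 weeks equals full adherence, yet its denominator runs from LTT start, so a gap of 2 or more days before the first dose puts a fully adherent patient with no as-needed tablets below the cut

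*SAP*

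**What the plan says.** SAP 4.8.1 gives average exposure in tablets per 4 weeks as "derived as 4*cumulative rimegepant exposure/time in the LTT period"; SAP 5.2.3 repeats the formula for the exposure subgroups. SAP 5.3 sets the origin: "LTT start date/time: Earliest complete date during the treatment epoch in the eDiary". The first dose is a separate date: "Study drug first dose date/time: Earliest complete date where subjects indicated that they took medication during the treatment epoch in the eDiary". In 4.8.1, time on rimegepant and total patient-years start at the first dose, so the section uses two origins for exposure.

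The 4-week tablet counts also start at LTT start. SAP 5.5 states that "LTT study days are used in analyses of migraine days and exposure, and are calculated from LTT start as follows", and the worked example in 4.8.1 has "interval 1; LTT study days 1 to 28".

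SAP 2.1 describes the Baseline Visit as the point "where enrollment into the Long-Term Treatment (LTT) phase will commence". Protocol 4.3.2 says that at that visit patients are given the drug but "will be instructed they cannot take study medication until baseline laboratory results confirm study eligibility".

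SAP 4.2.6 lists "Average rimegepant exposure (tablets per 4 weeks) for EOD+PRN treated subjects" among its key factors, split at 14. It also defines a subgroup with at least 14 tablets per 4 weeks for at least 12 weeks. SAP 4.8.1 labels 12.6 and 11.2 tablets per 4 weeks as 90% and 80% compliance with every-other-day dosing.

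**The concern.** The threshold leaves no slack. If LTT time begins before dosing is allowed, the waiting days enter the denominator and cannot hold a tablet. A patient who takes every scheduled tablet and nothing else then lands below 14.

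Such a patient reaches the upper stratum only by adding as-needed tablets, which Protocol 4.1 permits for a migraine on a non-dosing day. The split then partly sorts patients by whether they had migraines to treat rather than by adherence to the schedule. It feeds the LFT tables and an eDISH plot (SAP 4.6.3.1), AE tables (4.8.2) and worst laboratory abnormalities (4.8.3). It also feeds the EOD+PRN migraine-day tables and scatter plots (4.6.3.5), where selection on migraine bears directly on the outcome.

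**Working it through.** **The plan's own figures.** One tablet every 2 days gives 28/2 = 14 per 4 weeks. 0.9 × 14 = 12.6 and 0.8 × 14 = 11.2, which match SAP 4.8.1. So 14 is 100% of schedule.

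**Inputs.** L = LTT length in days. Twelve weeks is 84 days; a Week 12 visit at day 85 ± 7, extrapolated from Day 15 and Day 29 in Protocol Table 2, gives 78 to 92. w = days from LTT start to first dose. The documents do not give w; 0 to 7 is assumed. The patient takes every scheduled tablet and no as-needed tablets.

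**Formula.** Doses fall on LTT days w+1, w+3, and so on, so tablets = ceil((L − w)/2) and the average is 28 × tablets / L. Since tablets ≤ (L − w + 1)/2, the average is at most 14(L − w + 1)/L. That is below 14 for every w ≥ 2, whatever L is. The count in interval 1 is ceil((28 − w)/2).

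**Results, L = 84:**

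| Gap w (days) | Tablets | Average, LTT origin | Intervals, LTT origin | Average, first-dose origin |
|---|---|---|---|---|
| 0–1 | 42 | 14.0 | 14/14/14 | 14.0–14.17 |
| 2–3 | 41 | 13.67 | 13/14/14 | 14.0–14.17 |
| 4–5 | 40 | 13.33 | 12/14/14 | 14.0–14.18 |
| 6–7 | 39 | 13.0 | 11/14/14 | 14.0–14.18 |

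Over the 15 end days 78 to 92, a gap of 2 to 7 days gives an average below 14 on all 15. A gap of 1 day gives at least 14 on 8 of 15, and a gap of 0 on all 15.

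**First-dose origin.** With D = L − w, the average is 28 × ceil(D/2)/D, which is never below 14 under full adherence. If w = 0, nothing changes.

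**The 12-week subgroup.** With the LTT origin and w from 2 to 7, this patient qualifies on none of the 15 end days. Numbering the intervals from first dose does not reliably help. At w = 3 and L = 84 the counts become 14/14/13, because only 81 days remain and the shortfall moves to interval 3. Re-anchored, the patient qualifies on 8 of 15 end days at w = 2, 7 at w = 3 and 3 at w = 7. Even at w = 0 the patient misses on 5 of 15 (days 78 to 82), where the origin plays no part.

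**The compliance cuts.** For L of 78 to 92 and w up to 7, the average stays above 12.6. The lowest case is w = 7, L = 79: 36 tablets, 28 × 36/79 = 12.76. An early stopper can fall below: w = 7, L = 56 gives 25 tablets and 28 × 25/56 = 12.5.

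**As-needed tablets that cancel the effect on the average.** At L = 84: 1 at w = 2–3, 2 at w = 4–5, 3 at w = 6–7. At L = 85 and w = 7: 4, since 28 × 43/85 = 14.16.

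**The case against.** The strongest objection is that the gap may not exist in the data. LTT start is tied to the eDiary treatment epoch, not to the Baseline Visit, and no section says when that epoch opens. SAP 4.8.1 has drug-use entries begin once the patient is found eligible, and Protocol Table 2 first marks dose entry at the eligibility phone visit. If the epoch opens then, the gap could be zero. This stands as a limit. The earlier opening is the likelier reading, because LTT enrollment begins at Baseline and daily diary use is described without a break, but it is inferred.

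The example is also narrow. These patients have a history of 4–14 moderate to severe attacks a month, and 1 to 4 permitted extra tablets offset gaps of 2 to 7 days. That stands too, and it is also how the upper stratum comes to be selected on migraine.

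Rounding rules are in the Core SAP, which is not among the documents. Rounding to integers would lift 13.67 to 14 but not 13.33.

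A reader might infer that adherent patients are labelled under-dosed. The SAP attaches no adherence label to the split at 14; its labels sit at 12.6 and 11.2, and completers with gaps up to 7 days stay above both. A reader might also infer that the every-other-day safety database is understated. It is not: safety tables report the whole EOD+PRN group, and the near-daily subgroup in SAP 4.2.6 takes in every EOD+PRN patient whatever the tablet count.

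**Conclusion.** The point holds in a conditional form. Given full adherence, no as-needed tablets and at least 2 days between LTT start and first dose, the planned average is below 14 at any LTT length. With LTT end at day 84 the shortfall is 0.33 tablets per 4 weeks at 2–3 days and 1.0 at 6–7 days. It rests on two assumptions: that the treatment epoch opens before dosing is permitted, and the length of the gap.

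The documents do not support the claim that every adherent every-other-day patient is misclassified, since gaps of 0 days, and 1 day when LTT has an even number of days, still average at least 14. Nor do they support a count of patients affected: about 200 is the planned size of the group, not an estimate. It would also be wrong to infer that moving the interval origin repairs the 12-week subgroup. That subgroup demands 14 tablets in each of three intervals within about 84 days, a separate cause.

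All affected outputs are descriptive, so the consequence is a harder-to-interpret stratum rather than a wrong test. The correction is worth making because it is cheap and harmless if the gap is zero.

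**What to change.** In SAP 4.8.1 and 5.2.3, for the EOD+PRN-only split at 14 (SAP 4.2.6) and the 12.6 and 11.2 compliance cuts, compute average exposure as 4 × cumulative tablets divided by (LTT end date − study drug first dose date + 1)/7. Show the compliance cuts on this basis in the EOD+PRN column only. Keep the LTT denominator for the average-exposure categories pooled across enrollment groups, so that no pooled table mixes the two.

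In SAP 5.3, state when the eDiary treatment epoch opens, and state the rounding applied at 14.

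Leave the 28-day intervals as they are. For EOD+PRN, read the subgroup of at least 14 tablets for at least 12 weeks beside the planned rows for at least 13 and at least 12 tablets. These rows capture 13/14/14 and 12/14/14, but not the 11/14/14 pattern at gaps of 6–7 days.

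Cost: short wording edits and a small programming change using dates already derived; no new data. There are three downsides. Two average-exposure denominators must be footnoted. The pooled category at 14 keeps the limitation for EOD+PRN patients. A first-dose origin also forgives any delay in starting that was the patient's own.
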